12.4.4 Overall Best Response Assessment

Each patient will be classified according to his "best response" for the purposes of analysis of treatment effect. Best response is determined as outlined in Section 12.9 from a sequence of overall response assessments.

12.5 Response Criteria for Neuroblastoma Patients

This study will use the revised International Neuroblastoma Response Criteria for disease assessment.⁵⁶ The updated response criteria incorporate current approaches to imaging of neuroblastoma, including functional imaging. Furthermore, a standardized approach to assessment of bone marrow involvement is included. The current INRC do **not** include methods of disease assessment that are less sensitive and/or specific for neuroblastoma (⁹⁹Tc bone scan and catecholamine levels).

Key sites and terms

Primary site: The primary site will be identified as a measurable lesion ≥ 10 mm in diameter as assessed by cross sectional imaging (CT or MRI scan). Primary site measurements must be recorded in millimeters (or decimal fractions of centimeters). The longest diameter of the primary tumor will be recorded at baseline. Serial measurements of the primary tumor will include assessment of tumor size in the same orthogonal plane at the time of each evaluation. In patients with bilateral adrenal lesions, response will be based on the sum of the longest dimensions of both adrenal lesions unless biopsy proves one to be ganglioneuroma rather than neuroblastoma/ganglioneuroblastoma. In patients with multi-focal non-adrenal disease, the largest

tumor will be considered the primary tumor. Response in additional lesions will be assessed as described below for metastatic lesions.

Tracer avidity (¹²³I-MIBG or FDG-PET) in the primary site will be recorded at baseline. The scan appropriate for serial disease assessments should be used at each disease re-evaluation timepoint (e.g. ¹²³I-MIBG avid primary lesions should be followed using ¹²³I-MIBG scans during therapy).

Malignant lymph nodes: To be considered pathologically enlarged and measurable, a metastatic lymph node must be ≥ 15 mm in short axis when assessed by CT or MRI scan (CT scan slice thickness recommended to be no greater than 5 mm). At baseline and in follow-up, only the short axis of a discreet lymph node will be measured and followed as per RECIST criteria. Patients with neuroblastoma may have conglomerate masses of non-discrete lymph nodes (i.e. multiple contiguous retroperitoneal nodes). When a short axis of a discreet node cannot be identified, a lymph node conglomerate can be measured using the longest diameter of the composite lesion. Tracer avidity of metastatic nodes will be recorded at baseline and during disease evaluations.

For the purposes of response assessment, target lesions are disease sites that are measurable (non-nodal soft tissue mass ≥ 10 mm in longest dimension or lymph node ≥ 15 mm in short axis) and tracer avid OR are biopsy positive for neuroblastoma or ganglioneuroblastoma. The sum of diameters of target lesions is defined as the sum of the short axis of discrete lymph nodes (i.e., cervical, axillary nodes) added to the sum of the longest diameters of non-lymph node soft tissue metastases.

Non-measurable disease: All other lesions (or sites of disease), including small lesions (longest diameter < 10 mm or pathological lymph nodes with ≥ 10 to < 15 mm short axis), are considered non-measurable disease. Bone lesions, leptomeningeal disease, ascites, pleural/pericardial effusions are considered non-measurable.

Bone lesions: Osteomedullary disease will be assessed using ¹²³I-MIBG scans or FDG-PET scans. Technetium bone scans are no longer used as part of the revised INRC and are not included as part of disease reassessments during this trial. The extent of tracer avid disease will be evaluated using the Curie scoring system (see Curie Scoring System). SPECT may be used to confirm the presence or absence of lesions in a given segment of the body. The absolute Curie score should be reported at baseline. A relative score (Curie score at the time of disease assessment divided by baseline Curie score) should be recorded at the time of each disease evaluation.

Bone marrow disease: Bilateral bone marrow aspirates and trephine biopsies are required at disease assessment timepoints. The extent of marrow involvement in all four samples should be recorded. Use of immunohistochemical staining for evaluation of trephine biopsies is strongly encouraged. The percentage of tumor infiltration of bone marrow space assessed by histologic evaluation of trephine/biopsies or counting the number of tumor cells in aspirates by cytology or immunocytology (recommended if available) divided by the number hematopoietic/mononuclear cells evaluated to obtain a percentage involvement (methodology described by Burchill et al.).⁵⁸ The bone marrow sample with the highest percentage of tumor infiltration is used for response assessment. If > 0% to $\le 5\%$ tumor infiltration is the highest percentage seen among samples obtained, the result should be recorded as minimal marrow disease.

12.5.1 Response Criteria

PRIMARY (SOFT TISSUE) TUMOR RESPONSE¹

RESPONSE	ANATOMICAL IMAGING + MIBG (FDG-PET²) IMAGING
Complete Response (CR)	 < 10 mm residual soft tissue at primary site, AND complete resolution of MIBG or FDG-PET uptake (for MIBG non-avid tumors) at primary site
Partial Response (PR)	 ≥ 30% decrease in longest diameter (LD) of primary site MIBG or FDG-PET uptake at primary site stable, improved or resolved
Progressive Disease (PD)	 > 20% increase in longest diameter taking as reference the smallest sum on study (this includes the baseline sum if that is the smallest on study), AND a minimum absolute increase of 5 mm in longest dimension³
Stable Disease (SD)	Neither sufficient shrinkage for PR nor sufficient increase for PD at the primary site

¹Not for use in assessment of metastatic sites

RESPONSE AT METASTATIC SOFT TISSUE AND BONE SITES

RESPONSE	ANATOMICAL IMAGING + MIBG (FDG-PET¹) IMAGING
Complete Response (CR)	 Resolution of all sites of disease defined as: Non-primary target and non-target lesions measure < 10 mm AND Lymph nodes identified as target lesions decrease to a short axis < 15 mm, AND MIBG uptake or FDG-PET uptake (for MIBG non-avid tumors) of non-primary lesions resolves completely
Partial Response (PR)	• ≥ 30% decrease in sum of diameters² of non-primary target lesions compared to baseline, AND all of the following:

² For ¹²³I-MIBG non-avid tumors

³ A mass that has not met PD measurement criteria but has fluctuating ¹²³I-MIBG avidity will not be considered progressive disease.

	 Non-target lesions may be stable or smaller in size AND No new lesions AND ≥ 50% reduction in MIBG absolute bone score (Relative MIBG bone score ≥ 0.1 to ≤ 0.5) or ≥ 50% reduction in number of FDG-PET avid bone lesions^{3,4}
Progressive Disease (PD)	 Any of the following⁵: Any new soft tissue lesion detected by CT or MRI that is also MIBG avid or FDG-PET avid; Any new soft tissue lesion seen on anatomic imaging that is biopsied and confirmed to be a neuroblastoma or ganglioneuroblastoma; Any new bone site that is MIBG avid; A new bone site that is FDG-PET avid (for MIBG non-avid tumors) AND has CT or MRI findings consistent with tumor OR has been confirmed histologically to be neuroblastoma or ganglioneuroblastoma; > 20% increase in longest diameter taking as reference the smallest sum on study (this includes the baseline sum if that is the smallest on study), AND a minimum absolute increase of 5 mm in sum of diameters of target soft tissue lesions; Relative MIBG score ≥ 1.2⁴
Stable Disease (SD)	Neither sufficient shrinkage for PR nor sufficient increase for PD of non-primary lesions

¹ Used for MIBG non-avid tumors

The post-infusion MIBG scan is not considered a diagnostic study for the purposes of respons assessment. Progressive disease should NOT be designated on the basis of this scan.

²Sum of diameters is defined as the sum of the short axis of discrete lymph nodes (i.e., cervical, axillary nodes) added to the sum of the longest diameters of non-lymph node soft tissue metastases. Masses of conglomerate non-discrete lymph nodes will be measured using longest diameter.

³ For patients with soft tissue metastatic disease, resolution of MIBG and/or FDG-PET uptake at the soft tissue sites is not required; all size reduction criteria must be fulfilled.

⁴Relative Curie score is the absolute score for bone lesions at time of response assessment divided by the absolute score for bone lesions at entry onto a clinical trial. MIBG-SPECT or MIBG-SPECT/CT may be used for scoring purposes but the same imaging methodology should be used for all evaluations. ⁵The post-infusion MIBG scan is not considered a diagnostic study for the purposes of response

BONE MARROW RESPONSE

RESPONSE	BONE MARROW STATUS ¹
Complete response (CR)	Bone marrow with no tumor infiltration upon reassessment, independent of baseline tumor involvement
Progressive disease (PD)	 Any of the following: Bone marrow without tumor infiltration that becomes > 5% tumor infiltration upon reassessment; or Bone marrow with tumor infiltration that increases by > 2 fold and has > 20% tumor infiltration upon reassessment.
Minimal disease (MD)	 Any of the following: Bone marrow with ≤ 5% tumor infiltration and remains > 0-≤ 5% tumor infiltration upon reassessment; or Bone marrow with no tumor infiltration that becomes ≤ 5% tumor infiltration upon reassessment; or Bone marrow with >20% tumor infiltration that has > 0-≤ 5% tumor infiltration upon reassessment.
Stable disease (SD)	Bone marrow with tumor infiltration that remains positive with > 5% tumor infiltration upon reassessment but does not meet CR, MD or PD criteria

¹Immunohistochemistry strongly encouraged

DETERMINATION OF OVERALL RESPONSE

RESPONSE	CRITERIA
Complete Response (CR)	All components meet criteria for CR
Partial Response (PR)	PR in at least one component and all other components are either CR, MD (Bone marrow), PR (Soft tissue or Bone) or Not involved (NI); no component with PD.
Minor Response (MR)	PR or CR in at least one component but at least one other component with SD; no component with PD.
Stable Disease (SD)	SD in one component with no better than SD or NI in any other component; no component with PD.
Progressive Disease (PD)	Any component with PD

NI = Not involved, site not involved at study entry and remains not involved; MD = Minimal Disease, for bone marrow assessment only.

Overall Best Response Assessment

Each patient will be classified according to his "best response" for the purposes of analysis of treatment effect. Best response is determined as outlined in Section 12.8 from a sequence of overall response assessments.

Primary Tumor	Soft Tissue and Bone Metastatic Disease (MIBG or FDG-PET or PET/MR)	Bone Marrow Metastatic Disease	Overall
CR	CR	CR	CR
	CR for one response component with either CR or NI for		CR
CR	CR	MD	PR
CR	PR	CR	PR
CR	PR	MD	PR
CR	PR	NI	PR
CR	NI	MD	PR
PR	CR	CR	PR
PR	CR	NI	PR
PR	CR	MD	PR
PR	PR	CR	PR
PR	PR	NI	PR
PR	PR	MD	PR
PR	NI	CR	PR
PR	NI	NI	PR
PR	NI	MD	PR
NI	CR	MD	PR
NI	PR	CR	PR
NI	PR	MD	PR
CR	CR	SD	MR
CR	PR	SD	MR
CR	SD	CR	MR
CR	SD	MD	MR
CR	SD	SD	MR
CR	SD	NI	MR
CR	NI	SD	MR
PR	CR	SD	MR
PR	PR	SD	MR
PR	SD	CR	MR
PR	SD	MD	MR
PR	SD	SD	MR
PR	SD	NI	MR
PR	NI	SD	MR
SD	CR	CR	MR
SD	CR	MD	MR
SD	CR	SD	MR
SD	CR	NI	MR
SD	PR	CR	MR
SD	PR	MD	MR
SD	PR	SD	MR
SD	PR	NI	MR
SD	SD	CR	
SD SD	SD NI	CR CR	MR MR
NI	CR	SD	MR
NI NI		SD SD	
NI NI	PR SD		MR
		CR	MR
SD	SD	MD MD	SD
NI	SD	MD MD	SD
SD	NI NI	MD MD	SD
NI	NI GD	MD	SD
SD	SD	SD	SD
SD	NI	SD	SD
NI NI	SD	SD	SD
NI	SD	NI	SD
NI	NI	SD	SD
	PD in any one component	nor at study enrollment and no PD for any component	PD Not Evalua

CR: Complete Response; MD: Minimal Disease; PR: Partial Response; MR: Minor Response; SD: Stable Disease; PD: Progressive disease; NI: not involved; site not involved at study entry and remains not involved

Curie Scoring Summary

[figure not shown]
Гable 1a. Scoring skeletal disease

Regions 1 – 9		
Scoring	MIBG uptake	
0	No MIBG uptake	
1	1 focal site	
2	> 1 focal site	
3	≥ 50% of a region	

Table 1b. Scoring soft tissue disease

Region 10 (Primary soft tissue site)	
Scoring	MIBG uptake
0	No soft tissue uptake
1	1 focal soft tissue site
2	> 1 focal soft tissue site
3	≥ 50% of a region (chest, abdomen)

Region	Site	Curie score
1	Head / Neck	
2	Cervico-Thoracic spine	
3	Ribs / Sternum / Clavicles/ Chest	
4	Lumbar / Sacral spine	
5	Abdomen/Pelvis	
6	Upper Extremity (Proximal)	
7	Upper Extremity (Distal)	
8	Lower Extremity (Proximal)	
9	Lower Extremity (Distal)	
10	Soft Tissue	
TOTAL	Total scores from Regions 1 - 10	

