12.4 Response Criteria for Patients with Solid Tumor and Measurable Disease

12.4.1 **Evaluation of Target Lesions**

Complete Response (CR): Disappearance of all target and non-target

lesions. Any pathological lymph nodes (whether target or non-target) must have reduction in short axis to <10 mm. If immunocytology is available, no disease must be detected by that methodology. Normalization of tumor markers if elevated at study enrollment (for patients with

neuroblastoma).

Partial Response (PR): At least a 30% decrease in the sum of the

diameters of target lesions, taking as reference the

baseline sum diameters

Progressive Disease (PD): At least a 20% increase in the sum of the

diameters of target lesions, taking as reference the smallest sum on study (this includes the baseline sum if that is the smallest on study). In addition to the relative increase of 20%, the sum must also demonstrate an absolute increase of at least 5 mm. (Note: the appearance of one or more new lesions is also considered progressions). Note: in presence of SD or PR in target disease but unequivocal progression in non-target or nonmeasurable disease, the patient has PD if there is an overall level of substantial worsening in nontarget disease such that the overall tumor burden has increased sufficiently to merit

discontinuation of therapy

Stable Disease (SD): Neither sufficient shrinkage to qualify for PR nor

sufficient increase to qualify for PD, taking as

reference the smallest sum diameters while on study

12.4.2 **Evaluation of Non-Target Lesions**

Complete Response (CR): Disappearance of all non-target lesions and

normalization of tumor marker level. All lymph nodes must be non-pathological in size (<10 mm

short axis)

Note: If tumor markers are initially above the upper normal limit, they must normalize for a patient to be considered in complete clinical

response.

Non-CR/Non-PD: Persistence of one or more non-target lesion(s)

and/or maintenance of tumor marker level above

the normal limits

Progressive Disease (PD): Appearance of one or more new lesions and/or

unequivocal progression of existing non-target lesions. Unequivocal progression should not normally trump target lesion status. It must be representative of overall disease status change,

not a single lesion increase.

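### The neuroblastoma nodal CR cut-off in Section 12.5.1 (short axis below 15 mm) conflicts with the protocol's own definition of nodal disease and its other CR cut-offs; the effect on the response count is narrow

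*Combined protocol and SAP*

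**What the plan says.** Section 12.5 makes a node measurable, and so a possible target, by size: "a metastatic lymph node must be ≥ 15 mm in short axis when assessed by CT or MRI scan". A measurable site is a target if it is also "and tracer avid OR are biopsy positive for neuroblastoma or ganglioneuroblastoma" in type, so avidity is not required. Smaller nodes still count as disease: "pathological lymph nodes with ≥ 10 to < 15 mm short axis), are considered non-measurable disease".

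The CR row for metastatic soft tissue and bone sites in Section 12.5.1 is introduced as requiring that disease has cleared everywhere. It joins three conditions with AND:

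- "Non-primary target and non-target lesions measure < 10 mm";
- "Lymph nodes identified as target lesions decrease to a short axis < 15 mm";
- complete resolution of MIBG uptake (or FDG-PET uptake, for non-avid tumors) in the non-primary lesions.

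The PR row requires a "≥ 30% decrease in sum of diameters² of non-primary target lesions compared to baseline", and nodes enter that sum by short axis: "The sum of diameters of target lesions is defined as the sum of the short axis of discrete lymph nodes".

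Section 12.4.1 says that for CR any pathological node, target or not, "must have reduction in short axis to <10 mm". Section 12.4.2 treats below 10 mm as the non-pathological size. Section 12.3 sends neuroblastoma patients without MIBG-positive lesions to the Section 12.4 criteria.

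**The concern.** A target node that stops at 14 mm satisfies the nodal CR bullet. Yet it lies inside the 10 to under 15 mm range that Section 12.5 calls disease, and it would fail CR under Section 12.4. A non-target node of 12 mm must fall below 10 mm under the first bullet of the same cell, while a target node that started larger may stay at 14 mm.

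The 15 mm figure is also the size at which a node becomes a target. The size condition therefore asks only that the node fall below its own entry threshold, and it adds almost nothing to the tracer condition beside it.

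CR and PR both count toward the primary endpoint. What is at stake is whether a small change in a node can supply a component CR that makes a patient a counted responder.

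**Working it through.** The plan gives no figure for this criterion. The check is a comparison of thresholds, followed by the overall-response table and the primary decision rule.

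**1. Thresholds side by side**

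| Place | Nodal size rule |
|---|---|
| 12.5, target entry | 15 mm or more |
| 12.5, non-measurable disease | 10 to under 15 mm |
| 12.5.1, CR, first bullet (lesions) | below 10 mm |
| 12.5.1, CR, nodal bullet | below 15 mm |
| 12.4.1 and 12.4.2, CR | below 10 mm |

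**2. Shrinkage needed, single target node.** Decrease = 1 − follow-up/baseline.

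- 15 to 14 mm: 1 − 14/15 = 6.7%. The CR size condition is met. PR by size needs at most 0.70 × 15 = 10.5 mm, so it is not met.
- 18 to 14 mm: 22.2%. 20 to 14.9 mm: 25.5%. Both give the same result.
- Upper limit of this zone: 15/0.70 = 21.4 mm baseline.
- With a cut-off of below 10 mm: 1 − 10/15 = 33.3%. Any target node that passes CR by size must then have shrunk by more than the 30% needed for PR.

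**3. Who is affected.** Under the Section 12.3 routing, a patient assessed by Section 12.5 has an MIBG-positive lesion somewhere.

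- If a metastatic site is avid, component CR requires that uptake to resolve completely. Size alone does not decide.
- If only the primary is avid, and the target node is biopsy-positive and non-avid with no other unresolved metastatic disease, there is no non-primary uptake to clear. Size alone decides the metastatic component.

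**4. Overall response in that second case** (table at the end of Section 12.5.1, marrow not involved, node 15 to 14 mm)

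| Primary | Metastatic component | Overall | Counted response? |
|---|---|---|---|
| PR | SD (cut-off below 10 mm) | MR | no |
| PR | CR (cut-off below 15 mm, as written) | PR | yes |
| SD | CR (as written) | MR | no |

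The call moves from non-response to response only when the primary itself responds. A primary PR needs a decrease of at least 30% in longest diameter. If the node shrinks by 30% or more, the component is at least PR by size and the patient in the first two rows is a responder under either cut-off.

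**5. Link to the primary decision.** The rule in Section 11.3.1 (at least 3 of 20) reproduces. The exact probability of success is 7.5% at a 5% response rate, within the stated alpha of 10%, and 90.9% at 25%, against the stated power of 90%.

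Suppose exactly one patient of the kind in step 3 is enrolled. That call is decisive when exactly 2 of the other 19 respond: C(19,2) p²(1−p)¹⁷ = 171 p²(1−p)¹⁷.

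- p = 5%: 17.9%
- p = 10%: 28.5%
- p = 25%: 8.0%

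At p = 5%, the chance of declaring success is 6.7% if that patient is a non-responder and 24.5% if a responder. The difference is the 17.9% above.

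**The case against.** **The tracer condition and the routing protect most patients.** This stands. A reader might infer that shrinking a node from 15 to 14 mm earns CR, or lifts overall stable disease to a response on size alone. The documents do not support that: uptake must resolve wherever a metastatic site is avid, patients without MIBG-positive lesions go to Section 12.4, and stable disease at the primary with metastatic CR is only a minor response.

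**Passing CR by size without passing PR does not prove an error.** This also stands. A 10 mm non-nodal lesion going to 9 mm meets the below-10 mm rule with a 10% decrease, and the same is possible up to 10/0.70 = 14.3 mm. An absolute CR cut-off combined with a percentage PR rule does this near the entry size. The 21.4 mm limit applies to a single target lesion, because PR uses the sum. The evidence is the conflict between thresholds.

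**The 15 mm figure has a rationale, or the first bullet already covers nodes.** Section 12.5 does tie 15 mm to pathological enlargement as well as measurability. But it then describes pathological nodes of 10 to under 15 mm as disease, so that wording cannot make 14 mm normal. If the below-10 mm bullet includes nodes, a 14 mm node fails CR, but the nodal bullet is then redundant and the row contradicts itself.

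**The patient is very rare.** This largely stands. Section 2.1.1 reports no HRAS single-nucleotide variant in a neuroblastoma set of 1,089 and one neuroblastoma among 109 HRAS-mutated cases elsewhere. The HRAS mutations it names from preliminary screening were six, in rhabdomyosarcomas. Confirmation (Section 12.8) and central review (Section 11.5) still apply, but they would use the same written cut-off.

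**Conclusion.** The inconsistency is real and can be shown from the protocol alone: the nodal CR bullet in Section 12.5.1 cannot be reconciled with the 10 to under 15 mm disease range in Section 12.5, the below-10 mm bullet in its own cell, or Sections 12.4.1 and 12.4.2.

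Its consequence is narrow. Size alone changes responder status only for a neuroblastoma patient with an MIBG-positive primary that responds, a biopsy-positive and non-avid target node that falls below 15 mm by less than 30%, and no other unresolved metastatic disease. In the case worked above, a minor response becomes a PR. Where uptake does resolve, the size condition adds almost nothing to it.

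A reader might take 8% to 29% as the chance that this flaw decides the trial. It is not: the figures assume that one such patient is enrolled and that the other 19 respond independently at a common rate. The documents give no enrollment probability, and their mutation counts suggest a small one. Severity is minor.

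**What to change.** Reconcile Sections 12.4.1, 12.5 and 12.5.1 by changing the nodal CR size criterion for metastatic sites in Section 12.5.1 to a short axis below 10 mm. First check it against the revised International Neuroblastoma Response Criteria that the protocol cites, which were not available for this review. If that source supports 15 mm, the protocol should instead state why a target node of 10 to under 15 mm counts as resolved, and say that the first CR bullet excludes nodes.

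The cost is one number in a table and a slightly stricter CR. Sample size, schedule and decision rule are unchanged.

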- 4.1.4 Disease Status: Patients must have radiographically **measurable** disease (See Section 12) at the time of study enrollment. Patients with neuroblastoma who do not have measurable disease but have MIBG+ evaluable disease are eligible. Measurable disease in patients with CNS involvement is defined as any lesion that is at minimum 10 mm in one dimension on standard MRI or CT.

Note: The following do not qualify as measurable disease:

- malignant fluid collections (e.g., ascites, pleural effusions)
- bone marrow infiltration except that detected by MIBG scan for

- neuroblastoma
- lesions only detected by nuclear medicine studies (e.g., bone, gallium or PET scans) except as noted for neuroblastoma
- elevated tumor markers in plasma or CSF
- previously radiated lesions that have not demonstrated clear progression post radiation
- leptomeningeal lesions that do not meet the measurement requirements for RECIST 1.1.
- 4.1.5 Performance Level: Karnofsky ≥ 50 for patients > 16 years of age and Lansky ≥ 50 for patients ≤ 16 years of age (Note: Neurologic deficits in patients with CNS tumors must have been relatively stable for at least 7 days prior to study enrollment. Patients who are unable to walk because of paralysis, but who are up in a wheelchair, will be considered ambulatory for the purpose of assessing the performance score.

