- Tumor Disease Evaluation should be obtained on the next consecutive cycle after initial documentation of either a PR or CR. Subsequent scans may restart 2 cycles after the confirmatory scan. If the institutional investigator determines that the patient has progressed based on clinical or laboratory evidence, he/she may opt not to confirm this finding radiographically.
- 4-A Neurological exam also required for CNS patients.
- 4-B Non- Hodgkin Lymphoma/ Histiocytosis patients are required to have PET scans within 2 weeks prior to start of therapy and should also be followed with PET scans if positive at diagnosis. Refer to Section 12.8
- Patients with neuroblastoma must have both CT/MRI and MIBG scintigraphy prior to the start of protocol therapy if the patient was enrolled with or has a history of having MIBG avid tumor. Otherwise the patient must have either FDG-PET/CT or PET/MR prior to the start of protocol therapy. For patients with neuroblastoma and measurable disease by CT or MRI, lesions should be measured and followed using the same modality (CT or MRI) in addition to MIBG or FDG-PET/CT. For patients with neuroblastoma and evaluable disease by MIBG scintigraphy, use the same modality (MIBG scintigraphy) to image and follow patients; CT/MRI are not required but may be performed as clinically indicated. Refer to Section 12.5 and Section 12.8:
- Bone marrow aspirate and/or biopsy only required in patients suspected of having bone marrow metastasis on the basis of history, symptoms, laboratory evaluation or other clinical data.
- Bone marrow aspirate and/or biopsy should be performed only when complete response or partial response is identified in target disease or when progression in bone marrow is suspected.
- 7. The medication diary should be collected and reviewed weekly during cycle 1 (medication). The medication diary should also be reviewed after completion of each treatment cycle and uploaded into RAVE.

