12.3 Response Criteria for Patients with Solid Tumors

See the table in Section 8.0 for the schedule of tumor evaluations. In addition to the scheduled scans, a confirmatory scan should be obtained on the next consecutive cycle following initial documentation of objective response.

As outlined, patients will be assigned to one of the following categories for assessment of response: a) solid tumor (non-CNS) and measurable disease (Section 12.4); b) neuroblastoma with MIBG positive lesions (Section 12.5); c) CNS tumor (Section 12.7); and d) lymphoma/histiocytosis (Section 12.8). Note: Neuroblastoma patients who do not

have MIBG positive lesions should be assessed for response as solid tumor patients with measurable disease.

Response and progression will be evaluated in this study using the revised Response Evaluation Criteria in Solid Tumors (RECIST) guideline (version 1.1) [Eur J Ca 45:228-247, 2009]. Key points are that 5 target lesions are identified and that changes in the largest diameter (unidimensional measurement) of the tumor lesions but the shortest diameter of malignant lymph nodes are used in the RECIST v 1.1 criteria.

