12.3.1 Definitions

12.3.1.1 Evaluable for objective response:

Eligible patients who receive at least one dose of protocol therapy will be considered evaluable for response. Evaluable patients who demonstrate a complete or partial response confirmed by central review before receiving non-protocol anti-cancer therapy will be considered a responder. All other evaluable patients will be considered non-responders

12.3.1.2 Evaluable Non-Target Disease Response:

Eligible patients who have lesions present at baseline that are evaluable but do not meet the definitions of measurable disease and have received at least one dose of protocol therapy will be considered evaluable for non-target disease response. The response assessment is based on the presence, absence, or unequivocal progression of the lesions.

12.3.2 Disease Parameters

12.3.2.1 Measurable disease: Measurable lesions are defined as those that can be accurately measured in at least one dimension (longest diameter to be recorded) as ≥ 20 mm by chest x-ray, as ≥ 10 mm with CT scan, or ≥ 10 mm with calipers by clinical exam. All tumor measurements must be recorded in millimeters (or decimal fractions of centimeters).

Note: Tumor lesions that are situated in a previously irradiated area might or might not be considered measurable. If the investigator thinks it appropriate to include them, the conditions under which such lesions should be considered must be defined in the protocol.

- 12.3.2.2 Malignant lymph nodes: To be considered pathologically enlarged and measurable, a lymph node must be ≥ 15 mm in short axis when assessed by CT scan (CT scan slice thickness no greater than 5 mm). At baseline and in follow-up, only the short axis will be measured and followed.
- 12.3.2.3 Non-measurable disease: All other lesions (or sites of disease), including small lesions (longest diameter < 10 mm or pathological lymph nodes with ≥ 10 to < 15 mm short axis), are considered non-measurable disease. Bone lesions, leptomeningeal disease, ascites,

pleural/pericardial effusions, lymphangitis cutis/pulmonitis, inflammatory breast disease, and abdominal masses (not followed by CT or MRI), are considered as non-measurable.

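### The neuroblastoma metastatic PR rule in Section 12.5.1 has no clause for patients who lack target lesions or bone disease, so literal scoring biases ORR slightly downward

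*Combined protocol and SAP*

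**What the plan says.** - **Eligibility (Section 4.1.4):** "Patients with neuroblastoma who do not have measurable disease but have MIBG+ evaluable disease are eligible".
- **Routing (Section 12.3):** neuroblastoma with MIBG-positive lesions is assessed under Section 12.5.
- **Target lesions (Section 12.5):** "For the purposes of response assessment, target lesions are disease sites that are measurable", and also tracer avid or biopsy positive. The same section adds: "Bone lesions, leptomeningeal disease, ascites, pleural/pericardial effusions are considered non-measurable".
- **Metastatic PR (Section 12.5.1):** a fall of at least 30% in the sum of diameters "of non-primary target lesions compared to baseline, AND all of the following". The list requires non-target lesions that are stable or smaller, no new lesions, and at least a 50% reduction in MIBG bone score (relative score 0.1 to 0.5) or in the number of FDG-avid bone lesions. Footnote 3 says that in patients with soft-tissue metastases the size criteria must all be met.
- **Metastatic CR (Section 12.5.1):** size limits on lesions and nodes, and "MIBG uptake or FDG-PET uptake (for MIBG non-avid tumors) of non-primary lesions resolves completely".
- **Overall response (Section 12.5.1):** the narrative rule for PR needs PR in at least one component. The grid (primary / metastatic / marrow; NI = not involved, MD = minimal disease, MR = minor response) scores NI/PR/CR, NI/PR/MD and NI/CR/MD as PR, NI/SD/NI as SD, and PR/SD/NI as MR.
- **Analysis (Sections 11.3.1, 11.4, 11.5 and 12.3.1.1):** responders are patients with CR or PR. Every eligible patient with one dose is evaluable, and those without a centrally confirmed CR or PR are non-responders. The primary cohort succeeds with at least 3 responses in 20, designed for 5% against 25% with alpha 10% and power 90%.

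**The concern.** The protocol deliberately enrols patients whose disease can be followed only by tracer uptake, then defines metastatic PR through a diameter that these patients do not have. If central review applies the rule as printed, a patient whose bone score falls by 60% counts as a non-responder in the primary endpoint. The rule has two further effects:

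- A patient with a responding measurable primary and bone-only metastases is scored MR, a non-response, unless the bone uptake resolves completely.
- A patient with soft-tissue metastases only has no bone score to halve, so the same conjunction blocks metastatic PR from the other side.

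With a threshold of 3 responses in 20, one misclassified response can decide the primary cohort. Neuroblastoma is also a listed expansion histology (Appendix VII), and its expansion cohort opens only with three responses in that histology.

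**Working it through.** **Step 1: follow one patient through the text.** Take a patient with MIBG-avid bone disease, nothing measurable, uninvolved marrow, and a bone-score fall of 60% (relative score 0.4).

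1. Section 4.1.4: eligible. Section 12.3: assessed under Section 12.5.
2. Section 12.5: bone lesions are non-measurable and target lesions must be measurable, so there are no target lesions.
3. Metastatic PR: the bone-score condition is met. The diameter condition cannot be shown, because a 30% fall from an undefined sum does not exist. The conditions are joined by AND, so PR is not reached.
4. Metastatic CR: not reached, because uptake remains.
5. No progression, so the component is SD. The grid gives NI/SD/NI = SD.
6. Sections 11.5 and 12.3.1.1: evaluable, non-responder.

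If uptake resolves completely, the CR size limits have nothing to apply to and the component is CR. Overall response is then CR, or PR through the NI/CR/MD row. Complete resolution is therefore the only route to response for such a patient.

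**Step 2: reproduce the design (Section 11.3.1).** For X ~ Binomial(20, p) and success if X ≥ 3:

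- P(X ≥ 3 | p = 0.05) = 0.0755, within the 10% ceiling.
- P(X ≥ 3 | p = 0.25) = 0.9087, in line with the stated 90%.

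**Step 3: size of the effect.** Let k of the 20 patients be ones for whom the rule blocks PR. Let q be the chance that such a patient is still scored a responder, and let the other 20 − k respond at 25%. Power is P(A + B ≥ 3) with A ~ Binomial(20 − k, 0.25) and B ~ Binomial(k, q). For k = 1 this is

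(1 − q) × P(A ≥ 3) + q × P(A ≥ 2), with A ~ Binomial(19, 0.25), P(A ≥ 3) = 0.8887 and P(A ≥ 2) = 0.9690.

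At q = 0.10: 0.9 × 0.8887 + 0.1 × 0.9690 = 0.8967.

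| k | q = 0 | q = 5% | q = 10% |
|---|---|---|---|
| 0 | 90.9% | 90.9% | 90.9% |
| 1 | 88.9% | 89.3% | 89.7% |
| 2 | 86.5% | 87.4% | 88.3% |
| 3 | 83.6% | 85.3% | 86.8% |

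Each such patient lowers the expected ORR by (0.25 − q)/20: 1.25 points at q = 0 and 0.75 points at q = 10%. With k = 1 and q = 0, the type I error falls from 0.0755 to 0.0665, so the error is in the conservative direction.

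**Step 4: how large k might be.** The documents give neither k nor q. Section 2.1.1 reports one neuroblastoma among 109 HRAS-mutated cases in one data set. It reports no HRAS single-nucleotide variant in a neuroblastoma set of 1089, where the 3 HRAS findings were copy-number events. The mutations listed in Appendix VIII are all single- or multi-nucleotide variants. Section 2.1.1 also says that relapsed neuroblastomas carry HRAS mutations, without a frequency. MIBG-only disease is a further subset, so k = 0 or 1 is the realistic case.

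**The case against.** The strongest reply is that the intent is conditional: each condition applies to the disease type present. Footnote 3 ties the size criteria to patients with soft-tissue metastases. The NI/PR/CR and NI/PR/MD rows show that PR without a primary is expected. A literal reading that also bars soft-tissue-only metastases is hardly what was meant. This is a good account of intent and it stands as such. But footnote 3 says what soft-tissue patients must meet; it does not exempt bone-only patients, and no other text supplies the condition. Section 12.5 names the revised international neuroblastoma criteria as its source; how that source scores bone-only disease is not shown in the protocol.

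A reader might infer stronger points that the documents do not support:

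- *These patients can never have a PR and can only dilute ORR.* Complete resolution of uptake gives CR, which counts, and NI/CR/MD is scored as overall PR.
- *A measurable primary with bone-only metastases is capped at MR.* If bone uptake resolves, the metastatic component is CR and the grid gives PR/CR/NI = PR.
- *They fall under the non-target rules.* Section 12.3.1.2 ("The response assessment is based on the presence, absence, or unequivocal progression of the lesions") and Table 2 have no PR category, but Section 12.3 already sends MIBG-positive neuroblastoma to Section 12.5.
- *They need no CT or MRI.* Footnote 4-C to Section 8.1 does say "CT/MRI are not required but may be performed as clinically indicated", but that concerns how MIBG-evaluable patients are imaged and followed. The same footnote requires CT/MRI as well as MIBG before treatment in MIBG-avid disease.
- *They cannot help open a neuroblastoma expansion cohort.* The trigger in Section 11.3.2 counts CR as well as PR.

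**Conclusion.** The defect in wording is real and touches the primary endpoint. As printed, Section 12.5.1 denies metastatic-component PR to patients with no target lesions and, read equally literally, to patients with no bone disease. ORR is biased downward, never upward.

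The likely effect is small: about 1 to 2 points of power for one such patient in 20, if 0 to 10% of them can be scored as responders and they would otherwise respond at the design rate of 25%. The count and the rate are assumptions, and the protocol's own frequency data suggest few such patients. The design calculation is sound, and power slightly under 90% in this scenario is not a design failure. This is a minor point, worth correcting because central review must apply a rule that does not say what was probably meant.

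**What to change.** In the PR row for metastatic soft-tissue and bone sites in Section 12.5.1, state that:

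- the 30% diameter condition applies when target soft-tissue lesions are present at baseline;
- the 50% bone-score or lesion-number condition applies when avid bone disease is present at baseline;
- both apply when both are present;
- no new lesions are allowed in any case.

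This agrees with footnote 3 and with the NI/PR rows of the grid. In the same edit, reconcile the NI/CR/MD = PR row with the narrative rule that overall PR needs PR in at least one component.

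The cost is a few lines of text. No scan, visit or form is added, because Section 12.5 already calls for the Curie score at baseline and at each disease evaluation. The change should be made before any affected patient is centrally reviewed.
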